7.2 Treatment by local medical doctor (LMD)

The registering investigator is responsible for all treatment decisions and for the collection and submission of the study data in accordance with the approved protocol.

(**Note:** Treatment with local MD is allowed as long as the patient is able to come back to the registering site for sample collections under IRB # 521-93 or IRB# 14-009163).

When it has been determined that a patient's malignant disease is stable or objective tumor regression has been observed and the patient is tolerating therapy without excessive toxicity at a stable dose level, the drug(s) may be sent with the patient for

administration by the patient's Local Medical Doctor (LMD). The registering physician retains responsibility for the patient.

In this case, a written statement outlining drug dosage, method of administration, follow-up tests required, and telephone number to call to discuss any questions with the registering investigator must be sent with the patient to provide necessary information to the LMD. The LMD will be required to supervise the administration of the study drugs as stipulated in the protocol and provide written documentation that the drug was administered.

The registering investigator is responsible for all treatment decisions and for the collection and submission of the study data in accordance with the approved protocol.

The responsible investigator will ensure the integrity of the local physician, facilitate drug accountability, and ensure that the LMD can rapidly communicate toxicity.

7.3 End of study

All patients in Cohort A, Cohort B, Cohort C and Cohort D enrolled on this clinical trial will be treated on this study only for 6 cycles from the time of registration. After this time, they will no longer be part of the study and will be taken off study but can continue on their current therapy or any other therapy as deemed appropriate by their physician.

Patients can then continue the therapy instituted beyond cycle 1 with any additional therapeutic agents as deemed appropriate by their physician and/or local physician.

8.0 Dosage Modification Based on Adverse Events

Any adverse event noted in the study and its resultant dose-modifications should be managed as per the prescribing information of lenalidomide, dexamethasone and/or pomalidomide as per which of these two drugs the adverse event is attributable to.

8.1 Lenalidomide Dose Modifications

Lenalidomide (Cycle 1: Day 1-14 Cycle 2-6: Day 1-21)	
Starting dose	25mg
-1	10 mg
-2	Discontinue

→ → Use the NCI Common Terminology Criteria for Adverse Events (CTCAE) version 5.0*
unless otherwise specified ← ←

CTCAE System/Organ/Class (SOC)	ADVERSE EVENT	AGENT	ACTION**
Investigations	Platelet count decreased Grade 4	Lenalidomide	
*Omit dose until AE has resolved to Grade 1 or better
 
 • Follow CBC weekly • If thrombocytopenia $<30,000/\text{mm}^3$ recurs, reduce dose by one dose level (by 5 mg) and continue therapy when platelet count $\geq 30,000/\text{mm}^3$ 
If, after lenalidomide has been omitted, and the AE does not return to \leqGrade 1 within 4 weeks, then the patient may continue on remaining agent(s) till the completion of maintenance and then proceed to off study

	Neutrophil count decreased Grade 4		
*Omit dose until AE has resolved to Grade 2 or better
 
 • Follow CBC weekly * If neutropenia has resolved to \leqGrade 2, resume dose at one level lower *If, after lenalidomide has been omitted, and the AE does not return to \leqGrade 2 within 4 weeks, then the patient may continue on remaining agent(s) till the completion of maintenance and then proceed to off study
Blood and lymphatic system disorders	Anemia Grade 4		
*Omit dose until AE has resolved to Grade 2 or better
 
 • Follow CBC weekly * If anemia has resolved to \leqGrade 2, resume dose at one level lower *If, after lenalidomide has been omitted, and the AE does not return to \leqGrade 1 within 4 weeks, then the patient may continue on remaining agent(s) till the completion of maintenance and then proceed to off study
	Febrile neutropenia \geq Grade 3		
 • Omit dose and follow CBC weekly • If neutropenia has resolved to \leqGrade 2, resume dose at same level with GCSF support (See Section 9.2)

CTCAE System/Organ/Class (SOC)	ADVERSE EVENT	AGENT	ACTION**
Cardiac disorders	Sinus bradycardia/ other cardiac arrhythmia Grade 2	Lenalidomide	Omit dose and follow at least weekly until resolution 
 • If AE resolves to \leqGrade 1, reduce dose by one dose level and continue therapy
	\geq Grade 3		
 • Discontinue study treatment and go off study
Vascular disorders	Thromboembolic event \geq Grade 3		
 • Omit dose and start anticoagulation; restart at investigator's discretion (maintain dose level)
Immune system disorders	Allergic reaction Grade 2-3		
 • Omit dose and follow at least weekly until resolution • If AE resolves to \leqGrade 1, reduce dose level and continue therapy
	Anaphylaxis Grade 4		
 • Discontinue study treatment and go off study
Skin and subcutaneous tissue disorders	Erythema multiforme \geq Grade 3		Discontinue study treatment and go off study
	Skin ulceration \geq Grade 2		Discontinue study treatment and go off study
	Other: Non-blistering rash Grade 3		
 • If Grade 3 omit dose and follow weekly until resolution • If AE resolves to \leqGrade 2 continue therapy
Other AEs	Other: Non-blistering rash Grade 4		
 • Discontinue study treatment and go off study
	Non-hematologic AE assessed as related to lenalidomide \geq Grade 3		
 • Omit dose and follow at least weekly until resolution • If the AE resolves to \leqGrade 2, implement one dose reduction step and continue therapy (per Table 8.1)

* Located at http://ctep.cancer.gov/protocolDevelopment/electronic_applications.ctc.htm

** Use the following to describe actions in the Action column:

- **Omit** = The current dose(s) for the specified drug(s) during a cycle is skipped. The patient does not make up the omitted dose(s) at a later time
- **Hold/Delay** = The current dose(s) of all drugs during a cycle is delayed. The patient does make up the delayed dose(s) when the patient meets the protocol criteria to restart drugs.
- **Discontinue** = The specified drug(s) are totally stopped.

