3.13 Measurable disease as defined in section 11.0

3.14 Provide written informed consent.

3.15 Patient must be considered for treatment with an IMiD containing regimen.

3.16 ECOG Performance Status (PS) 0, 1, 2 or 3 (Appendix I).

3.17 The following laboratory values obtained \leq 14 days prior to registration:

- Hemoglobin \geq 7.0 g/dL
- Absolute neutrophil count (ANC) \geq 1000/mm³
- Platelet count \geq 50,000/mm³

- Total bilirubin $\leq 1.5 \times$ upper limit of normal (ULN) unless due to Gilbert's syndrome, in which case the direct bilirubin must be $\leq 1.5 \times$ ULN.
- Alanine aminotransferase (ALT) and aspartate transaminase (AST) $\leq 3 \times$ ULN ($\leq 5 \times$ ULN for patients with liver involvement)
- PT/INR/aPTT $\leq 1.5 \times$ ULN OR if patient is receiving anticoagulant therapy and INR or aPTT is within target range of therapy
- Calculated creatinine clearance ≥ 45 ml/min using the Cockcroft-Gault formula below:

Cockcroft-Gault Equation:

$$\text{Creatinine clearance for males} = \frac{(140 - \text{age})(\text{weight in kg})}{(72)(\text{serum creatinine in mg/dL})}$$

$$\text{Creatinine clearance for females} = \frac{(140 - \text{age})(\text{weight in kg})(0.85)}{(72)(\text{serum creatinine in mg/dL})}$$

3.18 Negative pregnancy test done ≤ 7 days prior to registration, for persons of childbearing potential only.
NOTE: If the urine test is positive or cannot be confirmed as negative, a serum pregnancy test will be required.

3.19a Willing to return to enrolling institution for follow-up (during the Active Monitoring Phase of the study).

3.19b Willingness to provide mandatory blood and bone marrow specimens for correlative research (see Section 14.0).

3.19c Willing to follow the requirements of the Pomalyst® REMS program

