8.4 Pomalidomide–Related Treatment Modification Guidelines for Adverse Events

8.41 Pomalidomide Dose Modifications

Pomalidomide (Cycle 1: Day 1-21 Cycle 2-6: Day 1-21)	
Dose Level	
Starting dose	4 mg
-1	3 mg
-2	2 mg
-3	1 mg
-4	Discontinue

→ → Use the NCI Common Terminology Criteria for Adverse Events (CTCAE) version 5.0*
unless otherwise specified ← ←

CTCAE System/Organ/Class (SOC)	ADVERSE EVENT	AGENT	ACTION**
Investigations	Neutrophil count decreased If ANC $<1.0 \times 10^9/L$ or ANC $>1.0 \times 10^9/L$ (up to LLN) with fever (temperature $>38.5^{\circ}C$)	Pomalidomide	Omit pomalidomide dose. Follow CBC weekly. If neutropenia has resolved to \leq Grade 2 prior to Day 21 and fever has resolved, restart pomalidomide at next lower dose level and continue through Day 21 of a 28-day cycle. If febrile neutropenia is the only toxicity for which a dose reduction is required, G-CSF may be used and the pomalidomide dose maintained.

CTCAE System/Organ/Class (SOC)	ADVERSE EVENT	AGENT	ACTION**
Investigations	Platelet count decreased If platelet count $<30 \times 10^9/L$	Pomalidomide	Omit pomalidomide dose Follow CBC weekly Hold anticoagulation/antiplatelet therapy until platelets $\geq 50,000/mm^3$ If platelet count resolves to \leq Grade 2 prior to Day 21, restart pomalidomide at next lower dose level and continue through Day 21 of each cycle
Skin and subcutaneous tissue disorders	Rash maculopapular Grade 2 or 3	Pomalidomide	Omit pomalidomide dose; follow weekly If the AE resolves to \leq Grade 1 prior to Day 21, restart pomalidomide at next lower dose level and continue through Day 21 of each cycle
	Grade 3-4 Stevens –Johnson Syndrome	Pomalidomide	Discontinue pomalidomide and remove patient from all study treatment
	\geq Grade 3 Erythema multiforme	Pomalidomide	Discontinue pomalidomide and remove patient from all study treatment
	Erythroderma \leq Grade 3	Pomalidomide	Omit pomalidomide dose; follow weekly If the AE resolves to \leq Grade 1 prior to Day 21, restart pomalidomide at next lower dose level and continue through Day 21 of the 28-day cycle
	Rash, maculo-papular Rash, acneiform Grade 4	Pomalidomide	Discontinue pomalidomide and remove patient from all study treatment
Nervous system disorders	Peripheral sensory neuropathy Grade 3	Pomalidomide	Omit pomalidomide dose and follow at least weekly. If the AE resolves to \leq Grade 1 prior to Day 21, restart pomalidomide at next lower dose level and continue through Day 21

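### The platelet row of section 8.1 gives conflicting restart and stop instructions at the same count, and does not say how a patient whose baseline is already worse than Grade 1 is handled

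*Combined protocol and SAP*

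**What the plan says.** Section 3.17 sets absolute entry floors: "Platelet count \geq 50,000/mm³" and "Hemoglobin \geq 7.0 g/dL".

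Section 8.1, platelet row, is headed by a Grade 4 fall and contains three instructions:

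- Restart: "Omit dose until AE has resolved to Grade 1 or better".
- Recurrence: if a count below 30,000/mm³ "recurs, reduce dose by one dose level (by 5 mg) and continue therapy when platelet count" is at least 30,000/mm³. (The size of the dose step is a separate matter and is not taken up here.)
- Four-week test: if, with lenalidomide omitted, "the AE does not return to \leqGrade 1 within 4 weeks, then the patient may continue on remaining agent(s"), the patient eventually goes off study.

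The anemia row restarts at a lower standard, "If anemia has resolved to \leqGrade 2, resume dose at one level lower", but its four-week test uses the same Grade 1 level as the platelet row. The neutrophil row uses Grade 2 for both: its restart level is Grade 2 and its stop test applies if "the AE does not return to \leqGrade 2 within 4 weeks".

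None of these rows refers to the patient's baseline, although section 10.61 has anemia and platelet count graded at baseline and at each evaluation. Section 8.0 separately sends dose modification to the prescribing information of each drug. Grading is by CTCAE v5.0, which the protocol cites without printing its cut points.

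**The concern.** The restart and four-week lines of the platelet row are not limited to a first event. A recurrence that is again Grade 4 therefore falls under all three lines, and they do not agree. One site could resume lenalidomide at 40,000/mm³ under the recurrence line. Another could withhold it at the same count and, after four weeks, take it away. Section 8.0 adds a second possible authority and does not say which rule prevails.

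The second difficulty is baseline. Entry is set by an absolute count, while the four-week test is set by a grade. If the grade lies above the entry floor, a patient can recover everything lost since enrollment and still meet the condition for losing the drug.

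What is at stake is how patients are treated in cycles 2-6, and whether sites treat like patients alike.

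**Working it through.** The plan states no figure to reproduce, and no sample size or error rate enters. The check compares the lines with each other. The Grade 1 floor is written F and varied, because the documents do not give it.

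**Inputs.** Entry floors: 50,000/mm³ and 7.0 g/dL (3.17). Recurrence level: 30,000/mm³ (8.1). First-event and four-week level: Grade 1, so F (8.1). Cycle 1 length: 21 days, with lenalidomide on Days 1-14 (7.1). Window for the visit before cycle 2: 3 days either side (4.0).

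**Step 1: the platelet lines against each other.** The conflict band runs from 30,000 to just below F. The baseline band runs from 50,000 to just below F.

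| Assumed F (/mm³) | Conflict band: continue and stay off | Eligible at entry but worse than Grade 1 |
|---|---|---|
| 50,000 | 30,000 to <50,000 | none |
| 60,000 | 30,000 to <60,000 | 50,000 to <60,000 |
| 75,000 | 30,000 to <75,000 | 50,000 to <75,000 |
| 100,000 | 30,000 to <100,000 | 50,000 to <100,000 |

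The conflict needs only F above 30,000. The baseline gap needs F above 50,000.

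**Step 2: one assumed floor worked through (F = 75,000).**

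| Count (/mm³) | Restart line met | Recurrence line met | Meets entry floor |
|---|---|---|---|
| 28,000 | no | no | no |
| 30,000 | no | yes | no |
| 45,000 | no | yes | no |
| 60,000 | no | yes | yes |
| 75,000 | yes | yes | yes |

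**Step 3: the anemia row at week 4.**

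| Grade at week 4 | Resume line (Grade 2 or lower) | Stop line (not Grade 1 or lower) |
|---|---|---|
| 1 | met | not met |
| 2 | met | met |
| 3 | not met | met |

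At Grade 2 the row tells the site both to resume and to stop. Loss of lenalidomide without a competing instruction needs a hemoglobin still worse than Grade 2. For a patient who returns to baseline, that means a baseline worse than Grade 2. If the Grade 2 floor is assumed to be 8 g/dL, this is 7.0 to <8 g/dL; if it is 7.0 g/dL, no eligible patient is in that position.

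**Step 4: timing against the response analyses.** Four weeks is 4 × 7 = 28 days. The visit before cycle 2 falls no later than day 21 + 3 = 24 of the planned schedule. Since 28 > 24, the four-week test cannot run out before the after-cycle-1 assessment, even for an event on Day 1.

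**The case against.** The best defense of the platelet row is that it describes a sequence. The row states no dose reduction for a first event, so the drug would return at the same dose and a stricter recovery level makes sense. After a recurrence the dose is lowered, so a looser level can be coherent. Resuming below an entry floor is not in itself an error, since eligibility and on-treatment limits serve different purposes. This is fair, and it is why no direction should be imposed. It does not remove the conflict, because the restart and four-week lines are not written as first-event rules.

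Baseline is also not a ceiling: sections 9.1 and 9.2 allow blood products and growth factors, so some patients may exceed their entry count. That stands. It makes failure at baseline possible rather than certain, and the row is silent on supported counts.

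Several stronger readings are tempting but not supported:

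- **Eligible anemic patients generally lose lenalidomide.** At Grade 2 the anemia row expressly says to resume; the defect there is a contradiction within the row.
- **The stop is permanent.** This is implied, but the four-week line does not use the protocol's defined term for total cessation.
- **Lost exposure passes for biological resistance in the biomarker work.** The primary endpoint and the race comparison (16.322) use response after one cycle, and 16.321 uses that same response rate, so the four-week test expires too late to act on them. Section 16.323 names no timepoint, but from cycle 2 other standard agents may be added anyway.
- **The milder pomalidomide rule shows an error.** Two drugs with separate tables may differ by design.
- **A number of affected patients.** The documents give neither the share with low baseline counts nor the rate of Grade 4 falls, and Cohorts C and D may receive pomalidomide instead.

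**Conclusion.** The point holds as a conflict in the instructions. In the platelet row, counts from 30,000/mm³ up to the Grade 1 floor can carry opposite instructions, on the sole assumption that this floor is above 30,000. The baseline gap holds on the further assumption that the floor is above 50,000: the band is 50,000 to <75,000 at an assumed floor of 75,000, and empty at 50,000. For hemoglobin, loss without a competing instruction is confined to patients whose baseline is worse than Grade 2.

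The consequence is inconsistent handling across sites and possible loss of lenalidomide in cycles 2-6. The after-cycle-1 analyses are little affected rather than wholly immune: doses can still be omitted within Days 1-14, and the second determination required by section 11.2 may fall in cycle 2. The number of patients cannot be derived from the documents. This should be corrected, but it does not undermine the primary estimate.

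**What to change.** Reconcile the first-event, recurrence and four-week lines of the section 8.1 platelet row with each other, with the entry floor in 3.17 and with the reference to prescribing information in 8.0. Say to which event each line applies and which source prevails. State, in both the platelet and the anemia rows, how a patient whose baseline is already worse than Grade 1 is handled, and remove the resume/stop overlap in the anemia row. The thresholds, and the direction in which they are reconciled, are for the sponsor's clinicians to decide.

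The cost is an amendment to the wording of two table rows and a cross-reference. No new data are needed: section 4.0 already schedules blood counts at baseline and before each cycle, and 8.1 asks for weekly counts after these events.

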	Peripheral sensory neuropathy Grade 4	Pomalidomide	Discontinue pomalidomide and remove patient from all study treatment

CTCAE System/Organ/Class (SOC)	ADVERSE EVENT	AGENT	ACTION**
Immune system disorders	Allergic reaction Grade 2-3	Pomalidomide	Omit dose and follow at least weekly If the AE resolves to \leq Grade 1 prior to Day 15, restart at next lower dose level and continue through Day 21
	Allergic reaction Grade 4	Pomalidomide	Discontinue pomalidomide and remove patient from all study treatment
Vascular disorders	Thromboembolic event \geq Grade 3	Pomalidomide	Omit dose and start anticoagulation Restart at investigator's discretion (maintain dose level)
Endocrine disorders	Hyperthyroidism or Hypothyroidism \geq Grade 2	Pomalidomide	Omit pomalidomide for remainder of cycle, evaluate etiology, and initiate appropriate therapy Reduce the dose of pomalidomide by 1 dose level.
Other non-hematologic adverse event	Other non-hematologic \geq Grade 3	Pomalidomide	If the AE can be attributed to either of the drugs, pomalidomide should be discontinued at first instance b for recurrence of the same toxicity necessitating dose modification Omit pomalidomide dose. Follow at least weekly If the toxicity resolves to \leq Grade 2 prior to Day 21, restart pomalidomide at next lower dose level and continue through Day 21

* Located at http://ctep.cancer.gov/protocolDevelopment/electronic_applications.ctc.htm

** Use the following to describe actions in the Action column:

- Omit = The current dose(s) for the specified drug(s) during a cycle is skipped. The patient does not make up the omitted dose(s) at a later time
- Hold/Delay = The current dose(s) of all drugs during a cycle is delayed. The patient does make up the delayed dose(s) when the patient meets the protocol criteria to restart drugs.
- Discontinue = The specified drug(s) are totally stopped.

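### Section 8.1 defines a lenalidomide dose level two ways (a 25 mg, 10 mg, stop ladder and a 5 mg step), and its anemia row uses two different recovery grades

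*Combined protocol and SAP*

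**What the plan says.** Section 8.1 opens with the lenalidomide ladder: "Starting dose 25mg -1 10 mg -2 Discontinue". The adverse event table beneath it applies that ladder row by row.

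- **Platelets.** After a Grade 4 event, if counts below 30,000/mm³ recur, the instruction is to "recurs, reduce dose by one dose level (by 5 mg) and continue therapy when platelet count" has reached that threshold again.
- **Anemia, Grade 4.** The restart line reads "If anemia has resolved to \leqGrade 2, resume dose at one level lower". The next line lets the patient go on with the other drugs if lenalidomide has been omitted "and the AE does not return to \leqGrade 1 within 4 weeks". (In these quotes, \leq is the less-than-or-equal sign.)
- **Neutrophils, Grade 4.** Restart is also at Grade 2 or better, and the matching limit is "and the AE does not return to \leqGrade 2 within 4 weeks".
- **Other non-hematologic events.** The row sends the reader back to the ladder: "implement one dose reduction step and continue therapy (per Table 8.1").

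The pomalidomide rows in Section 8.41 refer to levels and give no milligram amount. The platelet row there says "Grade 2 prior to Day 21, restart pomalidomide at next lower dose level and continue through Day 21 of each cycle" and the endocrine row says "Reduce the dose of pomalidomide by 1 dose level". Section 8.0 refers all dose modifications to the prescribing information, but does not say whether that or the tables prevail if they differ.

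**The concern.** A dose-reduction table should give one dose for one event. Here the platelet row names a dose level and then gives it a size that the ladder above does not contain, so a site cannot follow both halves of the instruction. Two sites reading the section literally could give the same patient different doses after the same toxicity. Section 7.2 also lets local physicians supervise administration according to the protocol, which requires a single stipulated dose.

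The anemia row raises a lesser question. A patient at Grade 2 four weeks after omission satisfies the restart line and also meets the condition for having failed to recover.

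At stake are dosing consistency and safety after a recurrent low platelet count.

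**Working it through.** **Inputs.** The ladder (25 mg, 10 mg, Discontinue) and the 5 mg step are both from Section 8.1. The 21 lenalidomide dosing days per cycle in cycles 2-6 are from Section 7.1. The starting dose by creatinine clearance is from Section 7.12, and the eligibility floor of 45 ml/min is from Section 3.17.

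**Step 1: is any ladder step 5 mg?** Start to level -1: 25 − 10 = 15 mg. Level -1 to level -2: 10 mg to no drug. Neither step is 5 mg. At 5 mg a time it takes 15 / 5 = 3 reductions (25, 20, 15, 10) to reach the dose that the ladder reaches in one.

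**Step 2: the two readings of the platelet row.** Totals are for a full later cycle at the reduced dose, i.e. daily dose × 21 days. The full-dose total is 25 × 21 = 525 mg.

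| Current dose | Reading | New dose | Total per cycle | Share of 525 mg |
|---|---|---|---|---|
| 25 mg | 5 mg step | 25 − 5 = 20 mg | 20 × 21 = 420 mg | 420/525 = 80% |
| 25 mg | ladder | 10 mg | 10 × 21 = 210 mg | 210/525 = 40% |
| 10 mg | 5 mg step | 10 − 5 = 5 mg | 5 × 21 = 105 mg | 105/525 = 20% |
| 10 mg | ladder | Discontinue | 0 mg | 0% |

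Neither 20 mg nor 5 mg is on the ladder. Both can still be dispensed, because Section 15.12 lists 5, 10, 15 and 25 mg capsules (20 = 15 + 5). Supply would not expose the error.

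**Step 3: is a milligram step the convention elsewhere?** Rows that call for a dose reduction:

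- Lenalidomide (8.1), 6: platelets, neutrophils, anemia, Grade 2 arrhythmia, Grade 2-3 allergic reaction, other non-hematologic.
- Dexamethasone (8.31), 6: dyspepsia Grade 1-2, dyspepsia Grade 3 or higher, edema, confusion or agitation, muscle weakness, hyperglycemia.
- Pomalidomide (8.41), 8: neutrophils, platelets, Grade 2-3 rash, erythroderma, Grade 3 neuropathy, Grade 2-3 allergic reaction, thyroid, other non-hematologic.

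The total is 6 + 6 + 8 = 20. The lenalidomide platelet row is the only one that states a milligram step; the other 19 refer to a level or to the ladder.

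**Step 4: the anemia row beside the neutrophil row.**

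| Row | Restart grade | Grade required within 4 weeks |
|---|---|---|
| Neutrophils | 2 or better | 2 or better |
| Anemia | 2 or better | 1 or better |

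A patient whose anemia is Grade 2 at week 4 meets the restart condition and, read literally, the non-recovery condition too.

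**Step 5: patients with reduced renal function.** Those with creatinine clearance of 45 to 60 ml/min are eligible and start at 10 mg, with an option to go to 15 mg after two cycles. On the ladder, 10 mg is level -1, so a first reduction would mean stopping; 15 mg does not appear at all. The plan does not say whether this is intended.

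**The case against.** The strongest reply is that Section 8.0 already refers dose modifications to the prescribing information, so a site may never rely on the table alone. That source is outside the documents, so actual divergence between sites cannot be demonstrated. This limits the claim to what Section 8.1 says by itself. It does not resolve the contradiction, because Section 8.0 gives no order of precedence.

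On anemia, the row can be read in sequence: a Grade 2 patient has already restarted, so the four-week line covers only those still off drug, and in any case it permits rather than requires. That is a fair reading. The row does not state it, so this part is a mismatch to tidy, with no dose difference shown.

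On renal dosing, the ladder calls 25 mg the starting dose and never says that a 10 mg start counts as level -1. That is accepted, and the point is raised only as a clarification.

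The consequence is also narrow. It needs a Grade 4 platelet event, recovery and recurrence. Cycles 2-6 already allow added standard-of-care agents and discretionary dexamethasone. Omitted doses are not made up, so the cycle totals do not describe the cycle in which the event occurs. All of this stands and is why the point is minor.

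Finally, the row count does not prove intent, since 5 mg steps are feasible with the listed capsules. The platelet row also pairs a Grade 1 recovery condition with a 30,000/mm³ condition after recurrence, which removing the parenthesis would leave in place.

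**Conclusion.** The concern holds, at minor severity. Section 8.1 contradicts itself on the size of a lenalidomide dose level: recurrent platelets below 30,000/mm³ lead to 20 mg or 10 mg from 25 mg, and to 5 mg or no drug from 10 mg. The conflict lies in one of the six lenalidomide reduction rows. The anemia row's recovery grades do not match, with a softer consequence.

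The milligram totals assume a complete 21-day dosing period in cycles 2-6. The documents give neither the frequency of this platelet event nor the share of patients with clearance of 45 to 60 ml/min, so no number of affected patients is claimed. The sample size, the exact binomial intervals, the cycle 1 response endpoint and the stopping rule, which counts only non-hematologic events, are unaffected.

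**What to change.** 1. In the platelet row, delete the 5 mg parenthesis so that the row follows the ladder as the other rows do. If 5 mg steps are what the study team wants, rewrite the ladder to list them.
2. In the anemia row, change the four-week limit to Grade 2 or better, to match its restart line.
3. Add one line, as a clinical choice for the study team, on the reduction steps for patients who start at 10 mg or are raised to 15 mg under Section 7.12 (for example 15, 10, 5 mg, Discontinue). Alternatively, confirm that stopping after 10 mg is intended for them.

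While editing the platelet row, the team should also confirm that its two recovery conditions (Grade 1 or better, and 30,000/mm³ after recurrence) are both meant.

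The cost is two wording edits and one clarifying line in a routine amendment, with no statistical cost.

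### The lenalidomide table in 8.1 has no Stevens-Johnson row, so a severe related case at 25 mg can be restarted at 10 mg, while 8.41 ends all study treatment for the same event on pomalidomide

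*Combined protocol and SAP*

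**What the plan says.** Section 8.1 gives three lenalidomide dose levels: 25 mg, then 10 mg, then stop. Its skin rows cover erythema multiforme of Grade 3 or higher, skin ulceration of Grade 2 or higher, and non-blistering rash at Grade 3 and at Grade 4. For the first two, and for "Other: Non-blistering rash Grade 4", the action is "Discontinue study treatment and go off study". The last row of the table covers any "Non-hematologic AE assessed as related to lenalidomide" of Grade 3 or higher. It has no upper grade and no exception for skin reactions. Its action is to omit the dose, follow the patient and, if the event falls to Grade 2 or lower, "implement one dose reduction step and continue therapy (per Table 8.1".

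Section 8.41, for pomalidomide, has a separate row for "Grade 3-4 Stevens –Johnson Syndrome", with the action "Discontinue pomalidomide and remove patient from all study treatment".

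Section 15.17 includes Stevens-Johnson syndrome and toxic epidermal necrolysis in its list of rare lenalidomide toxicities (below 1%), which is restricted to important or life-threatening events. The nursing guidance in 15.194 also warns of Stevens-Johnson syndrome. Section 8.0 states the general rule that adverse events "should be managed as per the prescribing information of lenalidomide, dexamethasone and/or pomalidomide".

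**The concern.** Both drugs carry this risk in the protocol's own safety sections, but only the pomalidomide table says what to do about it. The lenalidomide table is not simply silent, because its last row catches the event and gives a restart instruction. It is also inconsistent with itself: Grade 4 non-blistering rash ends treatment, yet a Grade 4 Stevens-Johnson case outside the other skin rows can go back on drug.

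Cohorts C and D may receive either drug, so two patients in the same cohort with the same event could meet opposite rules. No reason is given for the difference. At stake is re-exposure after a severe skin reaction. The response-rate endpoint and its analysis are unaffected.

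**Working it through.** **Rule trace.** Take a related Grade 3-4 Stevens-Johnson case and follow it through each table.

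| Step | Lenalidomide 25 mg (8.1) | Pomalidomide 4 mg (8.41) |
|---|---|---|
| Named row? | None | Yes, Grade 3-4 |
| Also meets erythema multiforme (Grade 3+)? | If yes, off study; otherwise go on | Not needed |
| Also meets skin ulceration (Grade 2+)? | If yes, off study; otherwise go on | Not needed |
| Rash rows? | No, limited to non-blistering rash | Not needed |
| Row that applies | General row, related non-hematologic Grade 3+ | Stevens-Johnson row |
| Action | Omit; if Grade 2 or lower, step down to 10 mg | Stop pomalidomide and all study treatment |

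Reading Stevens-Johnson syndrome into the erythema multiforme row of 8.1 does not work well, because 8.41 lists the two as separate events. The Grade 2-3 allergic reaction row in 8.1 does not help either, since it also restarts at a reduced dose.

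A patient whose dose is 10 mg under 7.12 (creatinine clearance 30 to 60 ml/min) is not affected: the next step in 8.1 is to stop.

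**How many patients.** The protocol gives no expected count, so there is no figure to reproduce. Inputs from the documents are the maximum accrual in 16.22 (A 32, B 32, C 63, D 63), lenalidomide as the only immunomodulator for Cohorts A and B in 7.1, and the rate below 1% in 15.17.

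- Certain lenalidomide patients: 32 + 32 = 64.
- Ceiling for Stevens-Johnson cases of any kind: 64 × 0.01 = 0.64.
- Each Cohort C or D patient given lenalidomide adds at most 0.01. If all 63 + 63 = 126 received it, the ceiling would be 0.64 + 1.26 = 1.90.

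Three further inputs are assumptions: 60% to 80% of patients are on 25 mg; 25% to 75% of cases are Grade 3-4, related, outside the other skin rows and later Grade 2 or lower; and 0.1% is used as an alternative true rate. For Cohorts A and B:

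- Patients on 25 mg: 64 × 0.60 = 38.4 to 64 × 0.80 = 51.2.
- Affected path at the 1% bound: 38.4 × 0.01 × 0.25 = 0.096 to 51.2 × 0.01 × 0.75 = 0.384.
- Affected path at 0.1%: 38.4 × 0.001 × 0.25 = 0.0096 to 51.2 × 0.001 × 0.75 = 0.0384.

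The range for Cohorts A and B is therefore about 0.01 to 0.38 expected cases.

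**The case against.** The strongest reply is section 8.0. It opens the dose-modification section, applies to any adverse event, and sends sites to the prescribing information; 15.17 does so again. Since 8.1 never names Stevens-Johnson syndrome, the label could be said to govern it. In addition, 7.2 leaves treatment decisions with the investigator, and 13.2 allows withdrawal for an adverse event. Most investigators would probably not rechallenge. This stands as a reason why a restart is not certain in practice. It does not remove the problem: these provisions permit stopping but do not displace a specific printed row that fits the event. The label is not reproduced, so no conflict with it is claimed. If 8.0 were enough, 8.41 would not have needed its own row. Expedited reporting under 10.41 (24 hours to 7 days) informs the sponsor but sets no dosing action.

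A second point is that the platelet row of 8.1 describes one dose level as 5 mg, which would suggest 20 mg rather than 10 mg. The general row refers to the table's own levels, so 10 mg is the better reading. Either reading means re-exposure.

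Third, the counts rest largely on assumptions. That is correct. A rate below 1% has no lower bound, the 0.01 to 0.38 range leaves out Cohorts C and D, and the 64 includes the allowance for cancelled or ineligible patients. Only the ceilings rest on the documents alone.

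Finally, the tables need not list every rare toxicity, and 8.41 itself lacks toxic epidermal necrolysis. That weakens 8.41 as a complete standard, but the remedy is to extend its row.

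**Conclusion.** The concern holds. As printed, 8.1 allows lenalidomide to be resumed at 10 mg after a Grade 3-4 Stevens-Johnson reaction, provided that the patient was on 25 mg, the event was related, no other skin row applied and the event improved to Grade 2 or lower. Section 8.41 ends all study treatment for the same event and grades. The missing row and the contradiction between the tables are certain from the text; whether any site would actually restart is not.

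The expected number of affected patients is well below one in Cohorts A and B, even at the 1% bound. The case for change rests on the seriousness of the event and the negligible cost of correcting it. It should be corrected at the next amendment.

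**What to change.** Add one row to the skin section of 8.1 for Stevens-Johnson syndrome and toxic epidermal necrolysis, using the action already in that table: "Discontinue study treatment and go off study". Extend the existing Stevens-Johnson row in 8.41 to include toxic epidermal necrolysis, which 15.17 and 15.27 list for the two drugs and which has a row in neither table. Without this, a toxic epidermal necrolysis case on pomalidomide would fall to that table's own general non-hematologic row, which also provides for a restart.

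The cost is one new row and one extended row in a protocol amendment. It adds no patients, visits or tests, and dosing for every other event stays as it is.
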